2.2.6. Statistical Analysis Plan

Initially, descriptive statistics will be used to analyse the data collected. The categorical data, gender and diagnosis, will be described using a frequency distribution table. Distribution of ratio data will be assessed using the Shapiro-Wilk test. Normally distributed ratio data will be described using mean and standard deviation, whereas non-normally distributed data will be described using median and interquartile range. Finally, the ordinal data, attenuation imaging score and sonographer appraisal will be described using a frequency distribution table with numbers and percentages, with the mode used to describe the central tendency. Inferential statistics will determine the agreement between the sonographer appraisal and attenuation imaging score, with the manufacturer cut-off values being used to create ordinal-level data. The statistical test to determine inter-rater agreement with ordinal data is kappa (McHugh, 2012). Weighted kappa will be used as this takes

into account the level of inter-rater disagreement (Sim and Wright, 2005), which in this study could be a minor inter-rater disagreement such as mild steatosis versus moderate steatosis rating as opposed to normal versus severe steatosis rating which would be a more significant inter-rater disagreement.

The previously stated values recommended by Landis and Koch (1977) will be used to evaluate the level of agreement. The magnitude of kappa can be affected by the weighting scheme used (Sim and Wright, 2005); linear weighting will be used as quadratic weighting attaches too much importance to near agreements.

2.3. Study Outcomes

The value of Kappa will be used to assess the agreement. An interrater agreement of 0.80, a value widely accepted in healthcare as the minimum interrater agreement (McHugh, 2005) so this value will be used to confirm or reject the hypothesis.

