There will be no randomisation all participants will undergo the same study procedure, which will be carried out during a single, routine hospital visit, avoiding the need for participants to attend additional appointments. The assessment will be carried out by two experienced sonographers with a minimum of 10 years of abdominal scanning experience. Sonographer 1 will scan each participant, with Sonographer 2 reviewing the images later in the same conditions to avoid variation caused by lighting conditions. Both sonographers will be blind to the participant's history before completing the liver assessment to avoid any bias from past medical history. They will assess the liver using routine ultrasound, making their decision based on hepato-renal contrast, visualisation of the walls of the intra-hepatic veins and visualisation of the liver parenchyma (Hernaez et al., 2011, Ballestri et al. 2021). The sonographers will individually grade the liver as normal, mild, moderate or severely fatty, recording this on a case report form. The attenuation imaging function will then be switched on and the ultrasound machine will calculate the attenuation imaging scores, according to manufacturer guidance, which will be recorded on the case report form along with the participant's age, gender, and diagnosis. The BMI measurement will also be taken in the time around the participant's appointment and recorded on the case report form as BMI has an impact on image quality (Reynolds, 2011).

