2.2.5. Power Calculation

The statistical test to determine inter-rater agreement when data are at the ordinal level is kappa (McHugh, 2012). The degree of agreement ranges between -1 and 1.0; 1.0 infers complete agreement, and 0 less agreement than random chance, with negative values indicating disagreement. Assessment of the strength of agreement will be based on the limits described by Landis and Koch (1977) where ≤ 0 =poor, 0.01–0.20=slight, 0.21–0.40=fair, 0.41–0.60=moderate, 0.61–0.80=substantial, and 0.81–1=almost perfect agreement.

The sample size for kappa is calculated based on the need to detect a difference between levels of agreement. McHugh (2005) acknowledges that an agreement of 0.80 or above is more widely accepted in healthcare as the minimum interrater agreement, and a kappa of 0.59 and below an inadequate agreement. Using these values with a power of 90% and alpha set at 0.05, the sample size will be 95.

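### The 90% power in section 2.2.5 is for kappa 0.80 against 0.59, but section 2.3 decides at 0.80 itself, a rule met about half the time at a true kappa of 0.80

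*Combined protocol and SAP*

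**What the plan says.** Section 2.2.5 takes 0.80 as the accepted minimum agreement and "a kappa of 0.59 and below an inadequate agreement". It concludes: "Using these values with a power of 90% and alpha set at 0.05, the sample size will be 95". It does not say which value is the null, whether alpha is one- or two-sided, how participants are expected to spread over the four grades, or what pattern disagreements will follow.

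Section 2.3 gives the decision rule. It opens with "The value of Kappa will be used to assess the agreement", cites 0.80 as the accepted minimum, and ends "so this value will be used to confirm or reject the hypothesis". No hypothesis is stated there or elsewhere; section 1.2 gives a research question and section 2.1 gives aims.

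Section 2.2.6 plans linear-weighted kappa. It names no test against 0.59 and no confidence interval. It says that published agreement bands "will be used to evaluate the level of agreement"; section 2.2.5 lists the top two as "0.61–0.80=substantial, and 0.81–1=almost perfect agreement".

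**The concern.** The power calculation and the decision rule are about different comparisons. The 90% belongs to a test that separates 0.80 from 0.59. Such a test succeeds once the estimate is far enough above 0.59, which can happen well short of 0.80. The rule in section 2.3 puts the cut at 0.80 itself.

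A reader could easily take 90% as the chance that the study confirms its hypothesis if true agreement is 0.80. Under the rule as written that chance is about one half. The likely harm is a reported rejection when agreement sits exactly at the level the protocol calls the accepted minimum. Because the hypothesis is not written out, the choice between the 0.80 cut and a test against 0.59 could also be made after kappa is known.

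**Working it through.** **Inputs from the documents.** Kappa 0.80 and 0.59, power 90%, alpha 0.05, N=95 (2.2.5); linear weights (2.2.6); four grades (2.2.2, 2.2.4); cut at 0.80 (2.3).

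**Assumed, because the documents give none.** Six grade mixes (normal/mild/moderate/severe, in %): 25/25/25/25, 40/30/20/10, 50/25/15/10, 60/20/12/8, 70/15/10/5 and 80/10/7/3. Two disagreement patterns: a chance mixture (the two gradings coincide with probability kappa and are otherwise independent) and a latent bivariate normal. One sonographer is compared with the attenuation grade, with equal margins.

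**Step 1: the plan's own figure.** With 0.59 as null and two-sided alpha,

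n = [(1.96 × sd0 + 1.2816 × sd1) / (0.80 − 0.59)]²,

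where sd0 and sd1 are the per-participant standard deviations of kappa at 0.59 and 0.80. For equal grades, linear weights and chance mixture, the large-sample variance of weighted kappa gives sd0 = 0.6945 and sd1 = 0.5285:

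n = [(1.3612 + 0.6773) / 0.21]² = 9.707² = 94.2, rounded up to 95.

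So 95 can be reproduced, but the stated inputs do not fix it. Changing one choice at a time gives 75.1 (one-sided alpha), 84.1 (0.80 as null), 74.8 (unweighted), 146.5 (quadratic weights) or 54.6 (latent normal).

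**Step 2: where that powered test cuts.** In the setting that gives 95, the critical estimate is 0.59 + 1.96 × 0.6945/√95 = 0.730. At true 0.80 the standard error is 0.5285/√95 = 0.0542, and power is Φ((0.80 − 0.730)/0.0542) = Φ(1.29) ≈ 0.90. This is the rule that the 90% describes.

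**Step 3: the rule in 2.3, same setting.** With the cut at 0.80 and true kappa 0.80, the probability is Φ((0.80 − 0.80)/0.0542) = Φ(0) = 0.50. The numerator is zero, so a larger N does not change it. An estimate of 0.75 would pass the test in step 2 and fail the rule in 2.3.

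**Step 4: simulation of an estimate of at least 0.80** (N=95, 40,000 runs per scenario; ranges over the six mixes and two patterns):

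| True kappa | Probability the rule is met |
|---|---|
| 0.59 | 0.000 to 0.017 |
| 0.80 | 0.49 to 0.51 |
| 0.85 | 0.75 to 0.92 |
| 0.88 | 0.87 to 0.99 |

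The true kappa at which the rule reaches 90%, in the order of mixes listed above, is 0.863, 0.864, 0.867, 0.871, 0.878 and 0.890 under chance mixture, and 0.847, 0.850, 0.851, 0.853, 0.859 and 0.869 under the latent normal.

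**Step 5: the other reading.** If an ordinary lower 95% limit above 0.80 was meant, it is met in 0.040 to 0.085 of studies at true 0.80.

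**The case against.** *The reading is not forced.* The sentence in section 2.3 is incomplete and names neither an estimate nor a limit, and section 2.2.6 says "Inferential statistics will determine the agreement between the sonographer appraisal and attenuation imaging score", which could imply a test or interval. This stands as a caution. But the text speaks of the value of kappa and no interval is planned, so a cut on the estimate is the natural reading. The limit reading makes the mismatch larger, and a test against 0.59 would rescue the 90% only if section 2.3 said so.

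*The 50% is generic.* Any roughly unbiased estimate cut at its true value passes about half the time. That is true, and for that reason the figure says nothing against the sample size. It is also why 90% cannot be attached to this cut at true 0.80.

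*The research question is one of estimation.* It asks for the level of agreement, and kappa will be reported either way. This stands and limits the stake, but section 2.3 still announces a verdict.

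*A reader might infer that the bands contradict the 0.80 bar.* They need not: an estimate of 0.75 can be described as substantial and still fall below a pass mark. What is missing is a sentence saying which of the two decides.

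**Conclusion.** The point holds: the power in section 2.2.5 does not belong to the rule in section 2.3. At a true kappa of 0.80 the rule, read on the estimate, is met about 50% of the time rather than 90%. The 50% needs only an estimator centred near the true value. The 0.85 to 0.89 needed for 90% rests on the assumed mixes and patterns, so it is a range and not a property of the plan.

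Three stronger inferences are tempting and not supported:

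- That N=95 is wrong or too small. It reproduces under a reasonable set of assumptions. The documents give no grade mix from which a shortfall could be shown.
- That the rule lets inadequate agreement through. It is stricter than the powered test and confirms in under 2% at true 0.59.
- That the kappa estimate is compromised. It is not; only the confirm/reject verdict and the power statement are affected.

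**What to change.** In section 2.3, write out H0, H1 and one decision rule. In section 2.2.6, add a two-sided 95% confidence interval for linear-weighted kappa, on the logit scale or by another method whose error rate has been checked. In the scenarios tried, the logit interval covered 0.947 to 0.956 and its lower limit rejected a true 0.59 in 2.5% to 3.0%; the ordinary limit did so in 3.3% to 5.0%, against a nominal 2.5%.

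**Preferred.** Keep 0.80 as the bar, say that the estimate is compared with it, and replace the 90% in section 2.2.5 with the power of that rule: about 50% at true 0.80, and about 90% only at a true kappa of 0.85 to 0.89. State the assumed grade mix and disagreement pattern. A cut on the estimate is a threshold and not a 5% test, so alpha should not be attached to it. If the lower limit is meant instead, quote power at a stated true kappa above 0.80 (logit-scale limit at true 0.90: 0.21 to 0.80).

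**Alternative.** Make kappa ≤ 0.59 the tested null, judged by the lower confidence limit. Conclude only that agreement exceeds the inadequate level, and report the estimate and interval against 0.80 separately. This lowers the bar for the verdict: in the setting that gives 95, the comparison in step 2 is passed at an estimate of about 0.73.

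Do not use a test based on the variance at kappa 0.59. That variance depends on the unknown grade mix: under chance mixture the critical estimate runs from 0.73 (equal grades) to 0.80 (80/10/7/3), and a cut fixed at 0.73 rejects a true 0.59 in 1.8% to 8.5%.

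Add one sentence saying that the agreement bands are descriptive and do not decide the hypothesis.

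**Cost.** Wording in sections 2.2.5, 2.2.6 and 2.3 and one interval, with no extra patients. The preferred route makes the stated power less favourable. The alternative changes the standard for success, which is more than wording.

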2.4. Timescale

Please see attached Gant chart in Appendix 1.

2.5. Publication Policy

A copy will be made available for all participants, sponsors, collaborators, and research and development department.

The study will also be submitted for inclusion in the academic journal Ultrasound and results may be shared for learning within and outside the health board at conferences and events.

Data will be anonymised on collection so no individual will be able to be identified at publication. The study will form part of an MSc thesis submission.

3. Screening, Consent and Withdrawal

3.1. Screening Duties

[name], as the researcher and a member of the clinical team, will be responsible for screening potential research participants. All ultrasound requests are vetted for suitability by a Sonographer as part of their clinical role. The researcher will review requests for abdominal scanning during the normal vetting procedure.

3.2. Informed Consent Procedures and withdrawal

Any patient identified who meets the criteria will be sent a participant information leaflet with the appointment letter. The study will be discussed with patient during their appointment visit and written consent can be obtained, if the patient agrees to take part. Any patients given short notice appointments will be given a patient information leaflet on attendance at the department to read whilst waiting to be called in for their examination. They will then be asked to sign an informed consent form if they're willing to take part. The sonographer undertaking the scan, who will have undertaken training in informed consent, will receive consent from the patient rather than the researcher to avoid coercion.

If the participant wishes to be withdrawn, then they can do so at any time up until the data is pseudonymised for analysis.

If for whatever reason the measurements cannot be taken (due to body habitus, liver lesions, etc) then the reason will be recorded, and from this point, no further data will be collected. The other data will be retained to look for patterns in patient demographics in reject analysis.

4. Risk, Ethical Considerations and Confidentiality

4.1. Risk and Benefits

Risks to patients:

Attenuation imaging uses the same principles as conventional ultrasound.

Ultrasound is considered a generally safe imaging modality and details of the British Medical Ultrasound Society 'Statement for the General Public on the Safety of Ultrasound' (2017) will be made available in the information leaflet. Standard ultrasound safety practice will be adhered to as per the British Medical Ultrasound guidelines (2009). Bae et al. (2019) found that the attenuation imaging scoring increased the scan time by approximately two minutes, so the scan time should remain within the safe level and minimally impact the patient's time.

The only further impact on the patient's time will be in measuring the patients BMI which is not a time-consuming process.

The ultrasound scan will be reported in the usual manner using the sonographer's initial assessments. So, the attenuation imaging scoring will have no impact on the report produced for the referring clinician and, consequently, no impact on the patient's treatment or pathway.

Risks to staff:

Increased scan times, high patient BMI and repetitive exam types in a single session can also impact sonographers, causing work-related musculoskeletal disorders (Harrison and Harris, 2015). These factors are accounted for in site risk

assessments based on advice from the Society & College of Radiographers (2019) and in the project risk assessment (Appendix 1.); these will be followed to minimise risk to the operators.

4.2. Ethical Considerations

NHS REC approval will be sought for this study and confidentiality, anonymity and informed consent will be ensured throughout.

4.3. Patient & Public Involvement

Patients will not be involved in the development and dissemination of this study but will contribute to its conduct as participants and will be informed of the potential for dissemination of results via non identifiable reports and publications.

4.4. Confidentiality

Participants' signed informed consent forms and research data will be securely stored at all times. Research data will be pseudo-anonymised. GDPR regulations will be adhered to throughout and information governance approval will be sought prior to study commencement

4.5. Premature Termination or Suspension of Study

If premature study termination is required (eg due to insufficient protocol adherence or inability to recruit participants and collect study data), HDUHB R&D (as sponsor), RECx, and academic supervisors will be notified in writing.

4.6. Record Retention and Archiving

In line with health board policy for sponsored studies, study records will be archived for five years at the designated archiving facility.

4.7. Study Oversight

[name], as CI will be responsible for study oversight and will report any issues to HDUHB R&D (as sponsor), Wales REC 6 and academic supervisor.

4.8. Study Reporting

The CI will provide regular updates to the academic supervisor and HDUHB R&D team and will submit an end of study report to Wales REC 6

4.9. Safety Reporting

Any adverse events or serious adverse events occurring during the study visit will be recorded and reported to HDUHB R&D in line with standard procedures.

5. Appendix 1.

Participant flow chart.

Project Timeline	Apr-23				May-23					Jun-23					Jul-23					Aug-23				Sep-23				Oct-23				Nov-23				Dec-23			
	3	10	17	24	1	8	15	22	29	5	12	19	26	3	10	17	24	31	7	14	21	28	4	11	18	25	2	9	16	23	30	6	13	20	27	4	11	18	25
Discussion with Supervisor																																							
Ethics HDD																																							
Ethics UWE																																							
Introduction																																							
Literature review-Research																																							
Literature review-Write up																																							
Data collection																																							
Data Analysis																																							
Results-Conclusion																																							
Draft 1																																							
Condense to article																																							
Submission																																							
Deadlines																																							
	Jan-24					Feb-24					Mar-24					Apr-24																							
	1	8	15	22	29	5	12	19	26	4	11	18	25	1																									
Discussion with Supervisor																																							
Ethics HDD																																							
Ethics UWE																																							
Introduction																																							
Literature review-Research																																							
Literature review-Write up																																							
Data collection																																							
Data Analysis																																							
Results-Conclusion																																							
Draft 1																																							
Condense to article																																							
Submission																																							
Deadlines																																							

6. References

